5. CONSIDERATIONS FOR DATA ANALYSES AND DATA HANDLING CONVENTIONS

The primary analysis in this study is comparison between the treatment groups on the primary efficacy endpoint change from baseline in HbA_{1c} with MMRM, where missing data at Week 26 will be imputed. For the lyophilized drug product arm the imputation will be based on assumption of the missing at random (MAR) while for the liquid drug product arm the imputation will be performed assuming the worsening of 0.4 relative to what would be expected under MAR. Missing data handling and sensitivity analysis under different assumptions of missing mechanism for the primary endpoint can be found in [Appendix 6: Premature Withdrawals & Handling of Missing Data](#).

In the conduct of the study, specific measures will be put in place to prevent and minimize missing data due to treatment withdrawals, noncompliance, etc. Upon study completion, the characteristics (frequency, causes) of the missing data, especially as related to the key efficacy endpoints, will be examined to inform the sensitivity analysis and imputation methods concerning missing data.

[Table 1](#) provides an overview of appendices within the RAP for outlining general considerations for data analyses and data handling conventions.

Table 1 Overview of Appendices

Section	Component
11.1	Appendix 1: Protocol Deviation Management Plan and Definitions for Per-Protocol Population
11.2	Appendix 2: Time & Events
11.3	Appendix 3: Assessment Windows
11.4	Appendix 4: Treatment Periods
11.5	Appendix 5: Derived and Transformed Data
11.6	Appendix 6: Premature Withdrawals & Handling of Missing Data
11.7	Appendix 7: Values of Potential Clinical Importance
11.8	Appendix 8: Multicenter Studies
11.9	Appendix 9: Examination of Covariates, Subgroups & Other Strata
11.10	Appendix 10: Multiple Comparisons & Multiplicity
11.11	Appendix 11: Model Checking and Diagnostics for Statistical Analyses
11.12	Appendix 12: Sample Size Considerations
11.13	Appendix 13: Abbreviations and Trademarks
11.14	Appendix 14: List of Data Displays

6. STUDY POPULATION ANALYSES

6.1. Overview of Planned Analyses

Table 2 provides an overview of the planned study population analyses, with full details of data displays being presented in Appendix 14: List of Data Displays.

Table 2 Overview of Planned Study Population Analyses

Display Type	Data Display's Generated		
	Figure	Table	Listing
Randomization			
Randomization			Y
Subject Disposition			
Subject Disposition		Y	Y
Reasons for Screening Failures		Y	Y
Reasons for Withdrawal from Study		Y	Y
Reasons for Discontinuing Study Treatment		Y	Y
Protocol Deviations		Y	Y
Deviations Leading to Exclusions from PP Population		Y	Y
Inclusion and Exclusion Criteria Deviations		Y	Y
Demography and Baseline Characteristics			
Demographics and Baseline Characteristics		Y	Y
Race & Racial Combinations		Y	Y
Substance use		Y	Y
Medical Condition & Concomitant Medications			
Medical Conditions (Current/Past)		Y	Y
Concomitant Medication		Y	Y
Exposure and Treatment Compliance			
Exposure to Study Drug		Y	Y
Treatment Compliance		Y	Y

Note: additional tables, listings and figures will be provided in Appendix 14: List of Data Displays.

- Y = Yes display generated.

Following review of the data, additional analyses maybe conducted to further support the evaluation and interpretation of the data.

6.2. Disposition of Subjects

The number of subjects who were randomized and the number of subjects within each population (ITT, Safety, PP, PK) will be summarized for each treatment group. A summary of subjects randomized by geographic region, and site will also be provided by treatment group.

The numbers and percentages of subjects who completed the study, discontinued the study, and discontinued the study treatment, along with reasons for discontinuation, will be summarized by treatment group. Additionally, among subjects who completed the study the number and percentage of subjects who continued into the open-label extension study, and did not participate in the open-label extension study will be also summarized and tabulated.

Subject status by visit summary will be provided.

Subject disposition data will be listed as well. All disposition summaries will be based on the all randomized subjects.

6.3. Protocol Deviations

As described in Section 4.1, all significant protocol deviations, those leading to exclusion from PP population, and all inclusion/exclusion criteria deviations will be summarized and listed, separately.

6.4. Demographic and Baseline Characteristics

Continuous variables such as age, body mass index, weight, and height will be summarized using descriptive statistics (n, mean, standard deviation, and median, minimum, maximum). Categorical variables including age group (<65, ≥65 years), sex, race, ethnicity, baseline weight category (<90 kg or ≥90 kg), and background antidiabetic therapy (diet and exercise or stable dose of metformin) will be summarized using numbers and percentages. Summaries will be presented by treatment group using the safety population.

Summary of substance (alcohol and tobacco) use will be provided, as well as a by-subject listing of data on alcohol and tobacco use. All summaries will be performed using the safety population.

6.5. Exposure to Study Drug

Descriptive statistics including the number of subjects, mean, standard deviation, median, minimum, and maximum for the duration of exposure to study drug will be presented by treatment group for the safety population. The duration of study drug exposure (in days) is defined as date of last dose of study drug - date of first dose of study drug + 1; missing doses will be ignored in this calculation. The total person time on study drug (in years) as defined in [Appendix 5](#) will also be displayed for each treatment group.

A by-subject listing of study drug administration will also be presented.

6.6. Treatment Compliance

Study treatment (both active drug and placebo injector) will be administered to the subject by the site personnel in the clinic at each scheduled weekly visit from Week 0 (i.e. Baseline/Randomization), Week 1 through Week 25. At each scheduled weekly visit, study treatment administration status (Yes/No), date/time of dose administered (if Yes) and reason no dose administered (if No) will be recorded in the Exposure eCRF page.

Treatment compliance (in percentage) will be based on the Exposure eCRF page and calculated as total number of doses administered divided by total number of doses expected over all available scheduled visits on treatment. Treatment compliance will be summarized for all subjects, as well as for subjects who discontinue study treatment early and subjects who complete study treatment. Treatment compliance will be also categorized as < 80% and \geq 80%, and summarized descriptively by treatment group.

Individual subject compliance information will also be listed. All summaries will be performed using the safety population.

Acceptable overall compliance for IP (albiglutide liquid and lyophilized) in this study will be \geq 80%.

6.7. Medications

Any prior and concomitant medication used during the study will be recorded and coded using GSKDrug Dictionary, which will be updated whenever available throughout the life of the study. Summary of all medications by treatment group and preferred term will be provided in relation to treatment phase (prior medication, concomitant medication, or post-therapy medication). Prior medications are those started and stopped before the first dose of randomized study drug. Concomitant medications are those taken at any time on or after the day of the first dose of randomized study drug and within 25 days after the last dose of randomized study drug, including those medications that started prior to randomization and continued into the treatment period. Post-therapy medications are those taken more than 25 days after the day of the last dose of randomized study drug.

All prior and concomitant medications will be listed using generic and verbatim terms. All summaries will be performed using the safety population.

6.8. Medical History

Subject data listings and summary tables will be provided for the following current and/or past conditions:

- cardiovascular medical history
- diabetes related medical history
- medical/surgical procedure history
- gastrointestinal (GI) medical history
- cancer history

- pneumonia medical history
- skin medical conditions
- thyroid medical history, thyroid cancer history, benign thyroid medical conditions
- thyroid cancer family history
- pancreatitis family history
- pancreatic cancer family history
- other medical history
- other medical/surgical surgery

The number and percentage of subjects with current and/or past medical histories listed above will be reported by treatment group. A summary of duration of diabetes disease history in years will be provided. The duration of diabetes disease history is calculated as the years lapsed between screening visit date and T2DM diagnosis date.

In addition, by subject listings of medical and family history status and all the medical conditions listed above will be provided.

All summaries will be performed using the safety population.

7. PRIMARY STATISTICAL ANALYSES

7.1. Efficacy Analyses

7.1.1. Overview of Planned Efficacy Analyses

The primary efficacy analyses will be based on the ITT population, unless otherwise specified.

Table 3 provides an overview of the planned efficacy analyses, with full details of data displays being presented in Appendix 14: List of Data Displays.

Table 3 Overview of Planned Efficacy Analyses

Endpoint/Parameter/ Display Type	Absolute							Change from Baseline						
	Stats Analysis			Summary		Individual		Stats Analysis			Summary		Individual	
	T	F	L	T	F	F	L	T	F	L	T	F	F	L
HbA _{1c} at Week 26				Y	Y		Y	Y	Y		Y	Y		Y

NOTES :

- T = Table, F = Figure, L = Listing, Y = Yes display generated.
- Stats Analysis = Represents TFL related to any formal statistical analyses (i.e. modelling) conducted.
- Summary = Represents TFL related to any summaries (i.e. descriptive statistics) of the observed raw data.
- Individual = Represents FL related to any displays of individual subject observed raw data.

Following review of the data, additional analyses maybe conducted to further support the evaluation and interpretation of the data.

7.1.1.1. Primary Analysis on Primary Efficacy Endpoint

The primary endpoint is the change from baseline in HbA_{1c} at Week 26. The primary analysis of the primary endpoint will be conducted using a mixed-effect model with repeated measures (MMRM) in the ITT Population. The primary analysis will include all HbA_{1c} values collected at scheduled visits from Week 4 up to Week 26. This will include values after hyperglycemia rescue and discontinuation from investigational product. Imputation under the non-inferiority null hypothesis for missing data will be incorporated [Koch, 2008]. Multiple imputation assuming missing at random (MAR) will be used to replace missing data of change from baseline of HbA_{1c} at Week 26 for all subjects in both treatment arms as a first step, and then to make all the imputed values for the liquid drug product arm worse by the non-inferiority margin 0.4.

Multiple imputation approach under MAR uses separate means and variance-covariance parameter estimation for each treatment arm (Carpenter and Kenward, 2013). Missing values for each subject will be imputed multiple times based on his or her own observed HbA_{1c} change from baseline values available and also based on the estimated means and variance-covariance from the treatment group where that subject is randomized to. This approach will be used for all missing data at Week 26 due to any reason including, but not limited to lost to follow-up and withdrawal consent. The details of implementing this multiple imputation approach are the following:

- **Step 1a:** Missing values at Week 26 will be imputed 100 times via SAS PROC MI (specifying BY treatment group, using MCMC statement with the option chain = multiple, including baseline and all post-baseline scheduled visits up to Week 26). As a result, 100 imputed datasets will be generated. Note: Only imputed values at Week 26 will be retained while the imputed values at other visits will be dropped from the imputed datasets.
- **Step 1b:** For each of the 100 imputed datasets from Step 1 the imputed values at Week 26 for the liquid drug product arm will be increased by 0.4.
- **Step 2:** Apply MMRM analysis as specified below for each of the 100 imputed dataset and save LSmeans (standard error) for each treatment arm at Week 26 and difference in LSmeans between treatment groups (standard error) from each of the 100 analyses.
- **Step 3:** Combine the 100 set of analysis results using Rubin's rules (Rubin, 1987) via SAS PROC MIANALYZE. The treatment differences, confidence intervals and p-values will be estimated by MODELEFFECTS and STDERR statement. Use the degrees of freedom (EDF) you would have if the dataset were complete.

The MMRM model via PROC MIXED will include HbA_{1c} change from baseline at post-baseline scheduled visits from Week 4 up to Week 26 as dependent variables; treatment, region (defined in [Appendix 8: Multicenter](#)), age category (<65 or ≥65 years), weight category (<90 or ≥90 kg), background antidiabetic therapy (diet and exercise or stable dose of metformin), visit week, treatment-by-week interaction and baseline HbA_{1c}-by-week interaction as fixed effects; baseline HbA_{1c} as a continuous covariate; and subject as a random effect. An unstructured covariance matrix will be used for the MMRM analysis, unless the model does not converge, in which case the covariance matrix will be decided upon model convergence status and the Akaike information criterion. Treatment effects estimates (and associated CI) of albiglutide liquid drug product will be evaluated within this MMRM model as least squares means contrasts relative to the lyophilized drug product.

The null hypothesis will be tested based on the 1-sided 97.5% confidence interval (with upper bound, equal to that of 2-sided 95% confidence interval) of the treatment difference at Week 26, which is estimated from the multiple imputation/MMRM (i.e. combined MMRM results from multiple imputation). If the upper bound of the confidence interval is less than or equal to 0.4%, non-inferiority will be concluded.

In addition, the observed HbA_{1c} and change from baseline HbA_{1c} will be summarized descriptively and presented graphically.

7.1.1.2. Supportive Analyses on Primary Efficacy Endpoint

- **Supportive analysis 1:**
The primary endpoint change from baseline in HbA_{1c} at Week 26 will be analysed using the same MMRM model as described in Section [7.1.1.1](#) but missing data are not explicitly imputed in this supportive analysis; although, there

is an underlying assumption that data is missing at random. All available scheduled post-baseline assessments from Week 4 up to Week 26 are utilized and, via modelling of the within subject correlation structure, the derived treatment difference at Week 26 is adjusted to take into account missing data. The MMRM analysis (using saturated fixed effects and an unstructured variance-covariance matrix) is considered appropriate as the supportive analyses, as it has been shown to give sensible answers to on-treatment questions in a range of practical situations [[Siddiqui,2009](#)].

The least squares means (and standard errors) of change from baseline in HbA_{1c} at Week 26 will be presented from the MMRM model. The least squares mean and the associated 1-sided 97.5% confidence interval (with upper bound, equal to that of 2-sided 95% confidence interval) of the treatment difference in change from baseline in HbA_{1c} will be reported at Week 26.

- **Supportive analysis 2:**

Analysis excluding HbA_{1c} data after hyperglycaemia rescue and discontinuation from study treatment will also be performed as supportive. It is not expected to have a substantial number of subjects who will require rescue and/or discontinue from study treatment and that number of subjects would be similar for both treatment arms. However, rescue medications given to subjects in this study may distort the estimates of the underlying treatment effect when HbA_{1c} change from baseline values at Week 26 are associated with rescue medications. To assess the impact of rescue and pure drug effect, analysis of pre-rescue data will be performed. The MMRM model will be similar to the one as described in Section [7.1.1.1](#). Results of this analysis at Week 26 will supplement the primary analysis. No imputation will be conducted for this supportive analysis.

- **Supportive analysis 3:**

The primary endpoint HbA_{1c} change from baseline at Week 26 will be analyzed using the same MMRM model as described in Section [7.1.1.1](#) in the PP population as a supportive analysis. No imputation will be conducted for this supportive analysis.

7.1.1.3. Analyses on Primary Efficacy Endpoint by Subgroups

The primary endpoint HbA_{1c} change from baseline at Week 26 will be examined by the following subgroups (also see [Appendix 9](#)) using the same multiple imputation/MMRM model approach for the primary analysis but also includes the subgroup- by-treatment-by-visit interaction term (as well as subgroup-by-treatment and subgroup-by-visit interaction terms) in the MMRM model step. The adjusted mean difference between treatment groups and associated 95% confidence interval for each level of the subgroup will be estimated from the combined MMRM results from the multiple imputations.

- Baseline HbA_{1c} category (< 8% or >=8%)

- Region (USA – North, USA – South Atlantic, USA – South Central and USA - West)
- Age category (<65 or >=65 years)
- Weight category (<90 or >=90 kg)
- Background antidiabetic therapy (diet and exercise or stable dose of metformin)
- Gender (male or female)
- Race (white or non-white)
- Ethnicity (Hispanic or non-hispanic)
- Duration of diabetes category (<5, 5 to 10 or >10 years)

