
 Same MMRM model as for the primary analysis
By-Subgroup Statistical Analysis

 The subgroup analyses will be performed using the same multiple imputation/MMRM model approach except in the MMRM step a treatment by subgroup interaction term is added to the model. The subgroups include baseline HbA_{1c} category, region, age category (<65 or ≥65 years), weight category (<90 or ≥90 kg), background antidiabetic therapy (diet and exercise or stable dose of metformin), gender, race, ethnicity and duration of diabetes category. Refer to Appendix 9: Examination of Covariates, Subgroups & Other Strata.

Model Specification

• Change from Baseline in HbA_{1c} = Baseline HbA_{1c} + Treatment + Region + Age Category + Weight Category + Background Antidiabetic Therapy + Visit Week + Treatment-by-Visit + Baseline HbA_{1c}-by-Visit Interaction + Subgroup (if not already in the model) + Subgroup-by-Treatment+ Subgroup-by-Visit + Subgroup-by-Treatment-by-Visit.• Refer to Appendix 11: Model Checking and Diagnostics for Statistical Analyses for SAS code
Sensitivity Statistical Analysis

• Refer to Appendix 6 Section 11.6.3.4: Sensitivity Analysis Under Missing Not At Random (MNAR)

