11.11. Appendix 11: Model Checking and Diagnostics for Statistical Analyses

11.11.1. Model Checking and Diagnostics for Statistical Analyses

1. Example SAS code for the primary efficacy analysis with imputation

Step 1a: Transpose the data horizontally and then impute data assuming missing at random (EFFIM)

```
PROC MI DATA= EFF OUT= EFFIM NIMPUTE=100 SEED=4408572;
  BY TRT01PN;
  MCMC CHAIN=multiple;
  VAR BASE CHG_W1 CHG_W4 CHG_W8 CHG_W12 CHG_W16 CHG_W20 CHG_W26;
  RUN;
```

Note: need to remove all imputed values before Week 26 and retain imputed values at Week 26 only.

Step 1b: Add 0.4 to the imputed value at Week 26 in the liquid product arm and transpose data in vertical structure (EFFIM2)

Step 2: Exclude HbA1c change from baseline at Week 1 and perform MMRM for each imputed dataset

```
Ods output SLICES=SLICE LSM SLICEDIFFS=SLICEDIFF;
```

```
PROC MIXED DATA= EFFIM ;
  BY _imputation_;
  CLASS USUBJID REGION WGTGR1 AGEGR1 PRIORDTX TRT01PN AVISITN;
  MODEL CHG= BASE REGION WGTGR1 AGEGR1 PRIORDTX TRT01PN AVISITN
  TRT01PN*AVISITN BASE*AVISITN/ DDFM=KR;
  REPEATED AVISITN/SUB=USUBJID TYPE=UN;
  SLICE TRT01PN*AVISITN/sliceby(AVISITN='26') means pdiff cl cov;
  RUN;
```

Step 3: Combine results using PROC MIANALYZE

```
PROC SORT DATA=SLICE LSM; BY TRT01PN IMPUTATION; RUN;
PROC MIANALYZE DATA=SLICE LSM EDF=CDF*;
BY TRT01PN;
MODELEFFECTS ESTIMATE;
STDERR STDERR;
RUN;
```

```
PROC MIANALYZE DATA=SLICEDIFF;
MODELEFFECTS ESTIMATE;
STDERR STDERR;
RUN;
```

*CDF=complete-data degrees of freedom. This is used to calculate the adjusted degrees of freedom for the combined results.

2. Example SAS code for the by-subgroup analysis of the primary endpoint with imputation

Follow the same steps as for the example SAS code for the primary analysis except in the step 2 additional interaction terms need to be added.

Subgroup variable: Baseline HbA1c <8% or >=8%

```
ods output SLICES=SLICELSM1 SLICEDIFFS=SLICEDIFF1;
PROC MIXED DATA= EFFIM;
  BY imputation;
  CLASS USUBJID REGION WGTGR1 AGEGR1 PRIORDTX TRT01PN AVISITN HBGR1;
  MODEL CHG= HBGR1 REGION WGTGR1 AGEGR1 PRIORDTX TRT01PN AVISITN
TRT01PN*AVISITN HBGR1*TRT01PN HBGR1*AVISITN
          HBGR1*TRT01PN*AVISITN/ DDFM=KR;
  REPEATED AVISITN/SUB=USUBJID TYPE=UN;
  SLICE HBGR1*TRT01PN*AVISITN/sliceby(AVISITN='26') means pdiff cl
cov;
RUN;
```

Subgroup variable: Baseline Weight <90 or >=90 kg

```
ods output SLICES=SLICELSM2 SLICEDIFFS=SLICEDIFF2;
PROC MIXED DATA= EFFIM;
  BY imputation;

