11.14.3. Efficacy Tables

Efficacy: Tables					
No.	Population	IDSL / TST ID / Example Shell	Title	Programming Notes	Deliverable [Priority]
HbA1c					
2.1.	ITT		Primary Analysis - Analysis of Change from Baseline in HbA1c (%) at Week 26 — With Imputation		
2.2.	ITT		Statistical Output Supporting the Primary Analysis of Change from Baseline in HbA1c (%) at Week 26		
2.3.	ITT		Supportive Analysis 1 - Analysis of Change from Baseline in HbA1c (%) at Week 26 — Without Imputation		
2.4.	ITT		Statistical Output Supporting the Supportive Analysis 1 of Change from Baseline in HbA1c (%) at Week 26 — Without Imputation		
2.5.	ITT		Supportive Analysis 2 - Analysis of Change from Baseline in HbA1c (%) at Week 26 — Without Imputation and Excluding Data after Hyperglycemia Rescue and discontinuation from study treatment		
2.6.	ITT		Statistical Output Supporting the Supportive Analysis 2 of Change from Baseline in HbA1c (%) at Week 26 — Without Imputation and Excluding Data after Hyperglycemia Rescue and discontinuation from study treatment		
2.7.	PP		Supportive Analysis 3 — Per Protocol Analysis of Change from Baseline in HbA1c (%) at Week 26 — Without Imputation		
2.8.	PP		Statistical Output Supporting the Supportive Analysis 3 of Per Protocol Analysis of Change from Baseline in HbA1c (%) at Week 26 — Without Imputation		

Efficacy: Tables					
No.	Population	IDSL / TST ID / Example Shell	Title	Programming Notes	Deliverable [Priority]
2.9.	ITT		Subgroup analysis: Analysis of Change from Baseline in HbA1c (%) at Week 26 by Baseline HbA1c Category — With Imputation		
2.10.	ITT		Subgroup analysis: Analysis of Change from Baseline in HbA1c (%) at Week 26 by Age Category at Randomization — With Imputation		
2.11.	ITT		Subgroup analysis: Analysis of Change from Baseline in HbA1c (%) at Week 26 by Region — With Imputation		
2.12.	ITT		Subgroup analysis: Analysis of Change from Baseline in HbA1c (%) at Week 26 by Weight Category at Randomization — With Imputation		
2.13.	ITT		Subgroup analysis: Analysis of Change from Baseline in HbA1c (%) at Week 26 by Background Antidiabetic Therapy — With Imputation		
2.14.	ITT		Subgroup analysis: Analysis of Change from Baseline in HbA1c (%) at Week 26 by Gender — With Imputation		
2.15.	ITT		Subgroup analysis: Analysis of Change from Baseline in HbA1c (%) at Week 26 by Race — With Imputation		
2.16.	ITT		Subgroup analysis: Analysis of Change from Baseline in HbA1c (%) at Week 26 by Ethnicity — With Imputation		

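### Subgroup HbA1c estimates inherit the liquid-arm +0.4 imputation penalty although they test no non-inferiority margin

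*SAP*

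**What the plan says.** The primary analysis (SAP 7.1.1.1) imputes missing Week 26 values within each arm under missing at random. Step 1b then applies a one-sided penalty: "the imputed values at Week 26 for the liquid drug product arm will be increased by 0.4". The lyophilized arm receives no shift (SAP 5).

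Three places carry this procedure into the subgroup analyses:

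- SAP 7.1.1.3 estimates a difference and 95% CI for each level of nine factors, "using the same multiple imputation/MMRM model approach for the primary analysis", with subgroup interaction terms added.
- The table in SAP 7.1.2 confirms that only the model step changes: "using the same multiple imputation/MMRM model approach except in the MMRM step a treatment by subgroup interaction term is added to the model".
- SAP Appendix 11 (11.11.1) tells the programmer: "Follow the same steps as for the example SAS code for the primary analysis", with extra interaction terms in Step 2.

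The nine subgroup displays, Tables 2.9 to 2.17 (the first is titled "Analysis of Change from Baseline in HbA1c (%) at Week 26 by Baseline HbA1c Category"), are all labelled as with imputation (SAP 11.14.3). No unshifted subgroup table is listed. The supportive and sensitivity analyses that drop or change the penalty cover only the overall comparison.

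The example code does not match the text. Step 1b names the shifted dataset EFFIM2, but the primary and subgroup models both read the Step 1a output: "PROC MIXED DATA= EFFIM".

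**The concern.** Imputing under the non-inferiority null has a specific purpose. It stops missing data from pulling the two arms together and making non-inferiority too easy to conclude. That reason applies to the one confirmatory test. SAP 7.1.1.3 states no margin and no test for the subgroups. It asks for an estimate and interval per level, which readers will use to judge whether the formulation difference is consistent.

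For that purpose, a penalty on one arm is a systematic shift against the liquid product. Its size depends on how many liquid-arm Week 26 values are missing in the level. If that share varies between levels, part of any apparent variation in treatment effect comes from the imputation rule. The plan tabulates missing-data patterns by treatment (Table 2.20) but not by arm within subgroup, so the tables do not give the figure needed to judge this.

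**Working it through.** **Inputs.** Penalty 0.4, liquid arm only (SAP 7.1.1.1, Step 1b). Margin 0.4, SD 1, expected difference 0, one-sided alpha 0.025, 133 per arm, 13% withdrawn early or lost, about 150 per arm randomized (SAP 11.12.1). The documents give no missingness by subgroup, so every unequal split below is an assumption.

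**The plan's own figure.** Noncentral-t power is 0.8993 at 132 per arm and 0.9015 at 133, so 133 for 90% power is reproduced. 133 / 0.87 = 152.9, or 153, consistent with approximately 150.

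**Shift in one level.** Let f be the fraction of liquid-arm subjects in the level whose Week 26 value is imputed. Adding 0.4 to those values raises the liquid mean, and so the difference, by 0.4 × f. This is exact for simple means and approximate for the covariate-adjusted MMRM.

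| f | Shift |
|---|---|
| 5% | 0.020 |
| 8% | 0.032 |
| 10% | 0.040 |
| 13% | 0.052 |
| 18% | 0.072 |
| 25% | 0.100 |

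**False gap between two levels** = 0.4 × (f₂ − f₁):

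- 13% and 13%: 0
- 8% and 18%: 0.040
- 10% and 25%: 0.060
- 5% and 25%: 0.080

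**Simulation.** 150 per arm, true difference 0, no subgroup effect, imputation by arm under missing at random, simple Week 26 means rather than the full MMRM. The added shift was 0.052 and 0.053 at 13%/13%, 0.033 and 0.073 at 8%/18%, and 0.021 and 0.099 at 5%/25%. Without the +0.4, the mean differences stayed within about 0.01 of zero.

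**Scale.** With SD 1, the standard error of a subgroup difference is √(2/75) = 0.16 at 75 per arm. For the interaction between two such halves it is √(4/75) = 0.23. A gap of 0.060 is 0.060 / 0.23 = 0.26 standard errors.

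**Small levels.** SAP 11.8.1 allows the largest region to be three times the smallest. If three regions are at that limit, the smallest has 300 / 10 = 30 subjects, about 15 of them on liquid. Each missing liquid-arm value there adds 0.4 / 15 = 0.027.

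**The case against.** Several points on the other side are sound.

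- **The driver is narrow.** A reader might infer that subgroups with more dropout will show a worse liquid effect. The documents do not support that. Subjects who stop treatment stay in the study (SAP 11.6.3.2) and are expected at Week 26, and observed values are not shifted. Missing values in the lyophilized arm attract no penalty. Only missing Week 26 values in the liquid arm matter, and they create false heterogeneity only if their share differs between levels.
- **13% may be too high.** The planning figure covers early withdrawal and loss to follow-up. With follow-up continued after treatment stops, the fraction missing at Week 26 could be lower, by an amount the documents do not allow one to estimate.
- **The effect is small.** A gap of about a quarter of a standard error would raise the rejection rate of a two-sided 5% interaction test only to about 6%, and SAP 7.1.1.3 reports no such test.
- **The shift can be traced.** It would be too strong to say that a reader could never separate it out. The listings of HbA1c and of subgroup values (SAP 11.14.8, Listings 132 and 134) would let someone with access count the imputed fraction and approximate the correction.
- **Using the primary method has a purpose.** It keeps the subgroup estimates on the same footing as Table 2.1, and the departure is conservative for the new product.
- **The code differs.** Run literally on EFFIM, the example code would leave the shift out of both the primary and the subgroup models.

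These points limit the size and certainty of the effect. They do not supply a reason for a null-hypothesis penalty in displays that test no null. The code mismatch is a discrepancy to correct; the SAP text states the +0.4 step plainly and is the better guide to intent.

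**Conclusion.** As the SAP text is written, each subgroup-level difference is shifted upward by about 0.4 times the liquid-arm fraction imputed in that level. This is about +0.05 if all of the planned 13% were missing at Week 26, and possibly less. With equal fractions the shift is uniform and there is no false heterogeneity. At 10% against 25%, an assumed split, the false gap is about 0.06, against an interaction standard error of about 0.23 (SD 1, two halves of 75 per arm).

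This is a modest, removable distortion. It is unlikely to change a subgroup conclusion by itself. A reader might infer that the primary result is compromised too. It is not: the penalty is deliberate and conservative there, and this point leaves it alone. The change is worth making because the bias is known, always runs against the liquid product and is cheap to remove.

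**What to change.** 1. Take the estimates and 95% CIs in Tables 2.9 to 2.17 from the Supportive Analysis 1 MMRM (no explicit imputation, no +0.4), with the subgroup interaction terms already specified in SAP 7.1.2.
2. Keep the penalised estimates as a second column, for consistency with Table 2.1.
3. Show the number with missing Week 26 HbA1c by arm within each subgroup level.
4. Do not simply drop Step 1b and use the Step 1a imputations. That model runs by arm on baseline and visit values, with no subgroup factor (baseline HbA1c enters only as a continuous variable). It pulls imputed values toward the arm mean and so dilutes real subgroup differences.
5. Correct EFFIM against EFFIM2 in SAP Appendix 11, so that it is clear which analyses, including the primary, use the shifted data.

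The cost is nine table reruns, and unpenalised subgroup estimates that will not average exactly to the primary estimate. The primary test, sample size and trial conduct do not change.
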